### 11.10.1. Changes to Study Visits and Study Procedures

- Where site staff resource is constrained due to COVID-19, IM dosing visits may proceed with limited or no other protocol-defined assessments (e.g. lab tests, questionnaires, etc.). If lab tests will be missed for more than one consecutive visit, the medical monitor must be contacted, to provide guidance for safety monitoring.
- For WOCBP, point of care pregnancy testing should be performed, prior to IM dosing.
- If central laboratory testing cannot be performed at a particular visit, and monitoring for safety is required, tests may be performed at an appropriately

authorised/accredited local laboratory (or other relevant clinical facility), if this can be done within local restrictions on physical distancing. The site should proactively inform the sponsor about such instances. Local laboratory results may be used to inform safety decisions. Results should be retained in source records.

- When on-site visits are reduced, it is important that the investigator continue collecting relevant clinical information, including adverse events, from the participant through alternative means, e.g. by telephone contact.
- There may be cases where the current principal investigator (PI) of a site is indisposed for a period and may need to delegate parts of his/her duties temporarily, e.g. to a sub-investigator. Any such changes should be documented in the site's source records. Any permanent changes in PI should be communicated to the sponsor.
- There may also be circumstances where immediate actions are required by the sponsor and/or investigator, outside of what is contemplated in the protocol, in order to protect a study participant from immediate hazard. Any such measures will be carefully documented and conducted in accordance with the National Competent Authority (NCA)/IRB/IEC regulations.

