## **9.3. Key Elements of Analysis Plan**

### **9.3.1. Primary Analyses**

For the primary efficacy analysis, virologic outcome for each participant in the Intent-to-Treat Exposed population will be calculated according to the FDA's Snapshot algorithm. The primary analysis at Week 48 will take place after the last participant has had their Week 48 viral load assessed, including a retest if required.

As defined by the Snapshot algorithm, HIV-RNA  $\geq 50$  copies/mL is determined by the last available HIV-1 RNA measurement while the participant is on treatment within the

analysis visit window of interest. In addition, participants without evaluable HIV-RNA data for the visit of interest and who discontinue from the maintenance phase for reasons not related to adverse event with HIV-1 RNA result at the time of discontinuation  $\geq 50$  copies/mL or who change study treatment not permitted per protocol before the analysis window are classified as having HIV-RNA  $\geq 50$  copies/mL.

For the primary efficacy analysis, the adjusted difference between the randomized arms for the proportion of participants with HIV-1 RNA  $\geq 50$  c/mL at Week 48 (according to the FDA snapshot algorithm) and its confidence interval will be calculated according to a stratified analysis with Cochran-Mantel Haenszel (CMH) weights. This analysis will adjust for the randomization strata (rederived for analysis to correct for stratification errors) according to prior exposure to CAB + RPV (0 weeks, 1-24 weeks, >24 weeks).

The CMH estimate of the common difference in rates across strata will be calculated as the weighted average of the strata-specific estimates of the difference in proportion between the two arms as follows:

- If  $n_k$  is the number of Q8W treated participants,  $m_k$  is the number of Q4W arm treated participants, and  $N_k = n_k + m_k$  is the total number of participants in the  $k$ th stratum, then the CMH estimate is given by

$$\hat{d}_{cmh} = \frac{\sum W_k \hat{d}_k}{\sum W_k}$$

where

$$W_k = \frac{n_k m_k}{N_k}$$

are CMH weights and  $\hat{d}_k$  are estimates of the differences in proportions between the two treatment arms,  $f_{Q8W} - f_{Q4W}$ , for the  $k$ th stratum.

The corresponding two-sided 95% CI will be calculated as:

$$\hat{d}_{cmh} \pm 1.96 \times \sqrt{\widehat{\text{var}}(\hat{d}_{cmh})}$$

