### **9.3.2. Secondary Analyses**

#### **9.3.2.1. Key Secondary Efficacy Analysis**

A key secondary analysis will evaluate the proportion of participants with HIV-1 RNA  $<50$  c/mL (according to the FDA's Snapshot algorithm) at Week 48 for the ITT-E population. Participants with last available HIV-1 RNA measurement less than 50 copies/mL while the participant is on treatment within the analysis visit window of interest are classified as responders; participants without evaluable HIV-RNA data for the visit of interest or who change treatment not permitted per protocol before the analysis window are considered non-responders. Full details on the Snapshot algorithm for computation of the proportion with HIV-1 RNA  $<50$  copies/mL will be contained in the RAP. The adjusted difference between the randomized arms for the proportions (Q8W – Q4W) and its confidence interval will be calculated according to a stratified analysis with Cochran-Mantel Haenszel (CMH) weights, as described for primary endpoint (Section 9.3.1).

A non-inferiority margin of -10% will be used for this secondary comparison, where if the lower limit of the 95% confidence interval (CI) of the difference between the rates (Q8W – Q4W) is greater than -10%, non-inferiority will be demonstrated.

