#### **11.8.7. Data Quality Assurance**

- All participant data relating to the study will be recorded on printed or electronic CRF unless transmitted to the sponsor or designee electronically (e.g., laboratory data). The investigator is responsible for verifying that data entries are accurate and correct by physically or electronically signing the CRF.
- The investigator must maintain accurate documentation (source data) that supports the information entered in the CRF.

- The investigator must permit study-related monitoring, audits, IRB/IEC review, and regulatory agency inspections and provide direct access to source data documents.
- The sponsor or designee is responsible for the data management of this study including quality checking of the data. Detailed information about study data collection and management process including systems used can be found in the study Data Management Plan.
- Study monitors will perform ongoing source data verification to confirm that data entered into the CRF by authorized site personnel are accurate, complete, and verifiable from source documents; that the safety and rights of participants are being protected; and that the study is being conducted in accordance with the currently approved protocol and any other study agreements, ICH GCP, and all applicable regulatory requirements.

Records and documents, including signed ICF, pertaining to the conduct of this study must be retained by the investigator for 25 years from the issue of the final Clinical Study Report (CSR)/ equivalent summary unless local regulations or institutional policies require a longer retention period. No records may be destroyed during the retention period without the written approval of the sponsor. No records may be transferred to another location or party without written notification to the sponsor

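### The COVID-19 appendix lets HIV-1 RNA be omitted at the Week 96 and Week 152 endpoint visits and gives local results no stated route to the eCRF or the Snapshot

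*Protocol*

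**What the plan says.** Protocol section 11.10.1 sets what may be dropped. The condition is "Where site staff resource is constrained due to COVID-19", and the permission is that "IM dosing visits may proceed with limited or no other protocol-defined assessments (e.g. lab tests, questionnaires, etc". Neither HIV-1 RNA nor the Week 96 and Week 152 visits are excepted. The only escalation is "If lab tests will be missed for more than one consecutive visit, the medical monitor must be contacted, to provide guidance for safety monitoring", so one missed visit triggers nothing, even if it is an endpoint visit.

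Local testing has its own condition: "If central laboratory testing cannot be performed at a particular visit, and monitoring for safety is required, tests may be performed at an appropriately" authorised or accredited local facility. The site is to tell the sponsor when this happens. On the results, the section says "Local laboratory results may be used to inform safety decisions. Results should be retained in source records".

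The analysis rules are in section 9:

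- Section 9.3.1: the outcome of 50 c/mL or more "is determined by the last available HIV-1 RNA measurement while the participant is on treatment" within the analysis window. Without evaluable data, a participant is counted there only after a non-AE discontinuation with RNA of 50 c/mL or more, or after a non-permitted change of treatment.
- Section 9.3.2.1: "participants without evaluable HIV-RNA data for the visit of interest" are non-responders for the below-50 endpoint.
- Section 9.3.2.2: both analyses are repeated at Week 96 and Week 152.

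On data capture, section 11.8.7 says "All participant data relating to the study will be recorded on printed or electronic CRF", with an exception for data sent to the sponsor electronically, such as laboratory data. The introduction to Appendix 10 (section 11.10) sets the aims of preserving scientific integrity and documenting COVID actions in the trial database.

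**The concern.** The waiver is written for safety and logistics, but the sample it allows sites to skip is also the efficacy endpoint. Someone who attends, is injected and has no RNA drawn at Week 96 or Week 152 is still on permitted treatment. Unless another RNA falls in the window, the Snapshot has nothing to classify.

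The effect differs by endpoint. For 50 c/mL or more, the participant drops out of the failure count but stays in the denominator. Both arms' rates shrink and so does their difference, which is the direction that favours non-inferiority. For below 50 c/mL, the same participant is charged as a non-responder.

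Where a local RNA is measured, section 11.10.1 mentions only safety use and source records. A site following that section alone has no instruction to enter the value, and a value that stays in source is not available to the algorithm. An analysis plan can set Snapshot rules, but it cannot recover a sample never drawn or a result never entered.

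**Working it through.** **Inputs.** From section 9.1: 510 per arm, true rates of 3% (Q8W) and 2% (Q4W) at 50 c/mL or more, a 4% margin and one-sided 2.5%. From sections 9.1 and 9.1.3: a 92% response rate. The protocol gives no missingness rate, so m = 2%, 5% and 10% are assumptions.

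**The plan's own figure.** With the unpooled Z statistic, power = Φ((0.04 − d)/SE − 1.96), where SE = √(p₁(1 − p₁)/510 + p₂(1 − p₂)/510). For 3% against 2%, SE = 0.00977, so (0.04 − 0.01)/0.00977 − 1.96 = 1.11 and power is 86.7%. The protocol states at least 85%, which reproduces.

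**Model for missing RNA.** A share m in each arm has no in-window RNA, unrelated to arm or viral load, and N stays 510. Observed rates at 50 c/mL or more become (1 − m)p, and so do observed response rates.

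**Counts at planning rates.** Expected failures are 510 × 0.03 = 15.3 and 510 × 0.02 = 10.2, together 25.5. Of these, 25.5 × 0.05 = 1.3 go uncounted at 5% missing and 25.5 × 0.10 = 2.6 at 10%. The expected difference falls from 1.00 to 0.95 and 0.90 points.

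**False non-inferiority at the margin (true 6% against 2%).** The asymptotic column uses the formula above. For m = 5%, the rates are 5.7% and 1.9%, d = 3.8 points and SE = 0.0119, so Φ(0.002/0.0119 − 1.96) = 3.7%. The exact column sums binomial probabilities over all outcomes for which the unstratified 95% upper bound is below 4%.

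| m | Observed rates | Asymptotic | Exact |
|---|---|---|---|
| 0% | 6.00% / 2.00% | 2.5% | 3.2% |
| 2% | 5.88% / 1.96% | 2.9% | 3.7% |
| 5% | 5.70% / 1.90% | 3.7% | 4.6% |
| 10% | 5.40% / 1.80% | 5.3% | 6.6% |

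The exact value exceeds 2.5% even with nothing missing. That excess belongs to the unstratified Wald interval, not to the appendix; only the rise down each column matters.

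**Below-50 endpoint.** A true 92% reads as 90.2%, 87.4% and 82.8% at m = 2%, 5% and 10%. If Q8W is truly 3 points lower (89% against 92%), exact power for the −10% comparison falls from 96.6% to 94.3%, 90.7% and 85.1%.

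**The case against.** The strongest reply is that nothing in section 11.10.1 bars a local result from the efficacy analysis. The wording is permissive. Section 9.3.1 takes the last available on-treatment RNA without requiring a central laboratory. Keeping a result in source does not exclude CRF entry, and section 11.8.7 read generally would send it there. This stands. A reader might infer that local results are confined to safety use, but the document does not say so. What remains is that 11.10.1 names no efficacy use and no database route, and should be reconciled with 9.3.1, 11.8.7 and the aims of Appendix 10.

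Second, section 9.3.1 includes on-treatment data from extra visits within a window, and window widths are left to the RAP. This also stands: a skipped sample becomes missing data only if no other RNA falls in the window. A reader might cite the Amendment 4 log entry on withdrawal visits to argue that only the key-visit sample counts. That is amendment-history text about a different situation and does not support the inference.

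Third, a reader might think a skipped blip retest also hides viremia. It does not: without the retest, the value of 50 c/mL or more remains the last available one and counts as failure.

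Fourth, section 11.10.6.1 records missed assessments as protocol deviations and summarises COVID deviations separately, and the two endpoints move in opposite directions. Heavy missingness would therefore be visible. Visibility does not supply the viral load.

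Finally, flexibility in a pandemic was deliberate, and missing-data rules usually belong in the analysis plan. That is fair for the rules. It does not cover which samples sites draw and where they record results, which this protocol fixes.

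**Conclusion.** The point holds in a limited form and should be corrected. Section 11.10.1 omits an exception for the endpoint RNA at Week 96 and Week 152 and gives no stated eCRF or Snapshot route for local RNA. Where no other in-window RNA exists, viremia goes uncounted on one endpoint and suppression is counted as non-response on the other.

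The size cannot be known from the protocol. At 5% to 10% missing, equal in both arms and unrelated to outcome, the exact unstratified chance of a false non-inferiority conclusion at the margin rises from 3.2% to between 4.6% and 6.6%. The planned analysis is stratified with the Sato variance, so these figures show direction and order of magnitude, not the trial's actual error rate. At planning rates, only one to three of about 25 expected failures would go uncounted.

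The affected analyses are the secondary Week 96 and Week 152 repeats; no claim is made about the Week 48 primary analysis. Nor can it be said that local results already held by sites would settle most cases. Where the waiver is used no sample need exist, and the protocol gives no split between skipped and locally tested visits.

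**What to change.** In section 11.10.1:

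1. Except HIV-1 RNA at Week 96 and Week 152 from the waivable assessments whenever the dosing visit takes place, or require it within the analysis window by a central or accredited local laboratory.
2. State that local HIV-1 RNA results are entered in the eCRF as well as kept in source records, in line with section 11.8.7.
3. State that an on-treatment, in-window local result is used in the Snapshot when no central result exists, with a central-only sensitivity analysis.

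The cost is a few sentences in Appendix 10, an eCRF page for local RNA and one sensitivity table. The downsides are one blood sample at a visit where staff are constrained, and local assays whose lower limit of quantification may differ from the central one; the sensitivity analysis addresses the latter.

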### **11.10.2. Changes to Informed Consent**

Informed consent should continue per normal procedure and as described in the main body of the protocol, to the extent possible. However, there may be circumstances where re-consent of participants is needed, and a physical signature on site is not possible. In these cases, alternative ways of obtaining such re-consent should be considered, such as the participant sending a picture of his/her written consent to the investigator, or the investigator contacting the participant by telephone or video call and obtaining verbal consent, supplemented with email confirmation.

Any updated informed consent form or other subject-facing materials should be provided to participants by e-mail, mail or courier before re-consent is obtained. Any consent obtained this way should be documented in source records and confirmed by way of normal consent procedure at the earliest opportunity when participants attend their next on-site study visit.

Any alternative informed consent procedure must be undertaken only after site IRB/Ethics Committee agreement and approval.

### **11.10.3. Permissible Use of Antiretroviral Therapy**

In order to minimize the risk of gaps in HIV-1 antiretroviral therapy (ART) for participants impacted by COVID-19 in the clinical trial, the following options can be considered with regards to ART dosing, in order of preference:

1. Where possible, and safe to do, please continue to prioritize IM dosing visits in order to keep the participants on the protocol-defined regimen
  - a. Qualified healthcare professionals (HCPs) trained on study procedures can administer IM injections outside of the study clinic setting (e.g. home, nursing facility, hospital), assuming this can be done safely, without compromising investigational product preparation/handling/storage/accountability requirements and done in accordance with local requirements. Please seek approval by the study team on a case-by-case basis.
2. If a participant is not able to attend an IM injection visit due to COVID-19 related restrictions, the gap in IM dosing should be covered with oral ART, until IM dosing can resume. Participants should be reminded of the importance of adhering with daily oral dosing. Two options can be approved for oral bridging therapy in consultation with the Medical Monitor, listed in order of preference:
  - a. Oral CAB + RPV
    - i. Investigator should request availability of oral CAB + RPV supplies, prior to pursuing option b.
  - b. Oral standard of care (SOC) commercial ART (prescribed locally)

#### Oral bridging with CAB + RPV

The protocol permits oral bridging to cover planned missed injections with oral CAB + RPV, only until IM dosing can be resumed. The start date of oral bridging should be within the dosing window for the missed IM dosing visit. This recommendation can be used to accommodate requests for oral dosing due to COVID-19. Oral bridging recommendations should be followed as per protocol Section 6.8.1. The process and required information for requesting oral bridging can be found in your Study Reference Manual. Please continue to reach out to your study medical monitor for approval of oral bridging, in order to document use and to ensure expeditious shipment of oral CAB + RPV to your site.

Participants who use oral CAB + RPV as short-term oral bridging are permitted to return to IM dosing, on protocol, once the COVID-19 conditions permit resumption of site activities.

The investigator should reach out to the medical monitor to confirm IM restart instructions, and to ensure the participant remains appropriate for resumption of IM dosing. If oral bridging with CAB/RPV is anticipated to continue for > 2 months, additional approval and guidance should be obtained from the medical monitor to continue with oral bridging therapy. Loading/Re-initiation doses of CAB + RPV IM may be required, depending on the length of oral bridging.

### Oral bridging with Standard of Care Antiretroviral Therapy (SOC ART)

For participants impacted by COVID-19, where the participant is unable to receive IM injections, and oral CAB + RPV is not available for use, oral bridging with any commercially available, guideline-recommended, SOC ART regimen is permitted. The start date of oral bridging should be within the dosing window for the missed IM dosing visit. Please reach out to your study medical monitor for approval of SOC ART as oral bridging, in order to document the use of commercially available SOC ART within the study. In order to assure that participants have access to SOC ART during short-term oral bridging, GSK may allow for reimbursement of SOC ART or copayments as needed.

Participants who use oral SOC ART as short-term oral bridging as a result of COVID-19 will not be considered formally withdrawn insofar as they wish to continue on the study. Individuals who bridge with SOC ART will be permitted to return to IM dosing, on study, once the COVID-19 conditions permit resumption of site activities.

The investigator should reach out to the medical monitor to confirm IM restart instructions, and to ensure the participant remains appropriate for resumption of IM dosing. If oral bridging with SOC ART is anticipated to continue for > 2 months, additional approval and guidance should be obtained from the medical monitor to continue with oral bridging therapy. Loading/Re-initiation doses of CAB + RPV IM may be required, depending on the length of oral bridging.

#### **11.10.4. Direct-To-Patient (DTP) Shipment of Oral Study IP**

If a participant is unable to travel to the clinic, either to receive IM injections or to be dispensed oral bridging, sites are encouraged to consider DTP shipments of drug, from the site, to the participant, to ensure access to medicines.

- If the study site is considering DTP shipment of oral CAB + RPV investigational product (IP), the site must first verify if DTP IP dispensing by investigators/hospital pharmacies is locally permitted and whether it requires regulatory and/or local ethics pre-approval, or post-hoc notification.
- The study participant should express his/her agreement for DTP shipment and the sharing of their personal information with any third-party couriers (as applicable), in accordance with local requirements. This agreement should be documented in source records.
- Oral CAB + RPV IP can be shipped at ambient temperatures via ground transport without a temperature monitoring device, with low risk of temperature excursions. Sites are encouraged to use discretion in determining the need for in-transit temperature monitoring based on the labelled storage requirements and the planned mode of transport and apply this as appropriate. Shipment of oral CAB + RPV via air courier continues to require appropriate temperature monitoring. For shipment conditions of oral medications other than oral CAB + RPV, please consult the product labelling.
- In all cases IP accountability must be maintained, and all DTP dispensing documentation should be reflected in source records and dispensing logs per GCP.

- Please refer to your CRA or local study manager for support with the DTP process, ensuring reference to current sponsor guidance and arrangement of a courier that can support shipment of IMP directly to participants.

#### **11.10.5. COVID-19 Experimental Agents**

If any treatments for COVID-19 are planned for a study participant, please consult with the study medical monitor to ensure that relevant drug interactions are considered and to ensure that continued study participation remains appropriate.

